The primary study objective is to assess the safety and tolerability of LCM as an adjunctive therapy for uncontrolled PGTCs in subjects with IGE during long-term exposure. Secondary objectives are to assess the efficacy of adjunctive LCM therapy during long-term exposure for the treatment of uncontrolled PGTCs in subjects with IGE, and to allow subjects who have completed SP0982 and eligible Baseline failures from SP0982 to receive LCM.

The primary safety variables are adverse events (AEs), subject withdrawals due to AEs, incidence of new seizure types, and increase in absence seizure days per 28 days or myoclonic seizure days per 28 days during the Treatment Period. Secondary safety variables are percentage of treatment-emergent marked abnormalities in hematology and chemistry parameters; percentage of treatment-emergent marked abnormalities in 12-lead electrocardiograms (ECGs); and percentage of treatment-emergent marked abnormalities in vital sign measurements (ie, blood pressure [BP] and pulse rate). Other safety variables include changes in hematology, chemistry, and urinalysis parameters, changes in 12-lead ECGs, and changes in vital sign measurements (ie, BP and pulse rate), including height and weight and physical (including neurological) examination findings. In addition, for pediatric subjects <18 years of age, safety will be evaluated using behavioral assessments (Achenbach Child Behavior Checklist [CBCL]), and cognitive function assessments (Behavior Rating Inventory of Executive Function®/Behavior Rating Inventory of Executive Function-Preschool Version® [BRIEF®/BRIEF-P®]). The seizure efficacy variables are evaluations of seizure frequency, based on information included in subject diaries. The health outcome variables, including the Patient Weighted Quality of Life in Epilepsy Inventory-Form 31 (QOLIE-31-P), the Pediatric Quality of Life Inventory™ (PedsQL™), the 3-level EuroQol-5 Dimension Quality of Life Assessment (EQ-5D-3L), healthcare resource use, the number of working or school days lost by subjects due to epilepsy, and the number of days with help from a caregiver due to epilepsy will be assessed for the first 2 years of treatment.

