### **4 STUDY VARIABLES**

#### **4.1 Safety variables**

##### **4.1.1 Primary safety variables**

The primary safety variables are:

- The incidence of TEAEs over the duration of the Treatment Period.
- Subject withdrawals due to TEAEs
- Incidence of new appearance of absence and/or myoclonic seizures during the Treatment Period
- An increase of up to 25%, >25% to 50%, >50% to 75%, and >75% in days with absence seizures per 28 days compared to the Prospective Baseline
- An increase of up to 25%, >25% to 50%, >50% to 75%, and >75% in days with myoclonic seizures per 28 days compared to the Prospective Baseline
- At least 50% worsening in days with absence seizures
- At least 50% worsening in days with myoclonic seizures

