### 6.3 Withdrawal criteria

Subjects are free to withdraw from the study at any time, without prejudice to their continued care. Investigators should contact the Medical Monitor whenever possible to discuss the withdrawal of a subject in advance. All subjects discontinuing treatment with LCM for any reason should taper as described in Section 7.2. All subjects who withdraw due to an AE must be followed until resolution of the event or until the event is considered stable.

Subjects **must** be withdrawn from the study if any of the following events occur:

1. Tapered subjects from SP0982 who enter EP0012 after the 125th event will be withdrawn at the enrollment visit and enter directly into the Safety Follow-Up Period without and ET Visit being performed in EP0012.
2. The subject develops second or third degree atrioventricular (AV) block.
3. The subject becomes pregnant, as evidenced by a positive pregnancy test.
4. The sponsor or a regulatory agency requests withdrawal of the subject.
5. The subject is unwilling or unable to continue, or the legal representative is unwilling or unable to allow the subject to continue in the study.
6. In the case of liver function test (LFT) results of transaminases (ALT and/or aspartate AST)  $\geq 3x$  ULN to  $< 5x$ ULN and total bilirubin  $\geq 2x$ ULN or transaminases (AST and/or ALT)  $\geq 5x$ ULN, LCM must be immediately discontinued, and the subject withdrawn from the study. The LFTs will be repeated as soon as possible, and in no case more than 1 week later.
7. Subject  $\geq 6$  years of age has actual suicidal ideation since last visit as indicated by a positive response "Yes" to either Question 4 or Question 5 of the "Since Last Visit" version of the C-SSRS. The subject should be referred immediately to a Mental Healthcare Professional and must be withdrawn from the study.
8. Subject is unable to tolerate at least the minimum LCM target dose of 4mg/kg/day (oral solution) or 200mg/day (tablets).

Subjects **may** be withdrawn from the study if any of the following events occur:

- The subject requires a medication that is not permitted (see Section 7.8).
- The subject is unable to manage the completion of the diary, demonstrates a questionable diary, or is noncompliant with the study procedures or medications in the opinion of the investigator.

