### 6.3.1 Potential drug-induced liver injury IMP discontinuation criteria

Subjects with PDILI must be assessed to determine if investigational medicinal product (IMP) must be immediately and permanently discontinued. In addition, all concomitant medications and herbal supplements that are not medically necessary should also be discontinued.

The PDILI criteria below require immediate and permanent discontinuation of IMP:

- ALT or AST  $\geq 5xULN$
- ALT or AST  $\geq 3xULN$  and coexisting total bilirubin  $\geq 2xULN$

Subjects with ALT or AST  $\geq 3xULN$  who exhibit temporally associated symptoms of hepatitis or hypersensitivity. Hepatitis symptoms include fatigue, nausea, vomiting, right upper quadrant pain or tenderness. Hypersensitivity symptoms include fever (without clear alternative cause), rash, or eosinophilia (ie,  $>5\%$ ).

If a nondrug-related cause for the symptoms can be confirmed, these subjects may resume IMP administration after discussion with the responsible UCB physician, but only when the requirements for rechallenge with IMP as provided in Section 10.3.1.2.1 are followed.

The PDILI criterion below allows for subjects to continue on IMP at the discretion of the investigator.

- Subjects with ALT or AST  $\geq 3xULN$  (and  $\geq 2x$  Baseline) and  $< 5xULN$ , total bilirubin  $< 2xULN$ , and no eosinophilia (ie,  $\leq 5\%$ ), with no fever, rash, or symptoms of hepatitis (eg, fatigue, nausea, vomiting, right upper quadrant pain or tenderness).

Evaluation of PDILI must be initiated as described in Section 10.3.1. If subjects are unable to comply with the applicable monitoring schedule, IMP must be discontinued immediately. See Section 6.3 for when and how to discontinue subjects from the IMP. See Section 8.2 for the procedures to be performed at the time of discontinuation.

Investigators should attempt to obtain information on subjects in the case of IMP discontinuation to complete the final evaluation. Subjects with PDILI should not be withdrawn from the study until investigation and monitoring are complete. All results of these evaluations and observations, as well as the reason(s) for IMP discontinuation and subject withdrawal (if applicable), must be recorded in the source documents. The CRF must document the primary reason for IMP discontinuation.

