#### 10.3.1.2.1 IMP restart/rechallenge (if applicable)

Rechallenge with a substance potentially causing drug-induced liver injury is dangerous, may be fatal, and must not occur.

Subjects who are immediately discontinued from IMP due to having met certain criteria for PDILI (as described in Section 6.3.1 and Table 10-3), but for whom an alternative diagnosis is confirmed, can rarely restart IMP. Rechallenge with IMP can occur only if ALL of the following requirements are met:

- The results of additional testing and monitoring described in Section 10.3.1.3 and Section 10.3.1.4 confirm a nondrug-related cause for the abnormal hepatic laboratory parameters and any associated symptoms (ie, a subsequent alternative diagnosis fully explains the hepatic findings).
- No alternative treatment options are available to the subject.
- The subject has shown clear therapeutic benefit from the IMP.
- Subject's ALT or AST elevations do not exceed  $\geq 3xULN$ .
- Subject's total bilirubin is  $<1.5xULN$ .
- Subject has no signs or symptoms of hypersensitivity.
- The rechallenge is approved by the UCB responsible physician and a hepatologist. The hepatologist must be external to UCB. It is recommended that the hepatologist be a local hepatology expert or the hepatologist treating the subject.

Subject agrees to the investigator-recommended monitoring plan.

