## 12.2 General statistical considerations

Descriptive statistics will be used to provide an overview of the primary, secondary, and other variable results. For categorical parameters, the number and percentage of subjects in each category will be presented. The denominator for percentages will be based on the number of subjects appropriate for the purpose of analysis. For continuous parameters, descriptive statistics will include number of subjects, mean, standard deviation (SD), median, minimum, and maximum.

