## 12.3 Planned safety and other analyses

### 12.3.1 Safety analyses

The incidence of all TEAEs, treatment emergent SAEs and TEAEs leading to premature discontinuation from study drug will also be summarized descriptively. Additional summaries will be provided by maximum intensity and relationship to study drug. All tables of TEAEs will include Medical Dictionary for Regulatory Activities primary System Organ Class and Preferred Term. Further details on the analysis of each variable will be given in the SAP.

Incidence of new seizure types, increase in days with absence seizure or myoclonic seizures per 28 days during the Treatment Period, and 50% worsening in days with absence seizures or myoclonic seizures per 28 days during the Treatment Period will be summarized.

Laboratory measurements as described in Section 10.3 and other safety measurements as described in Section 10.4 will be presented.

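### The protocol disagrees with itself on whether a subject stopped for a liver signal leaves the study, so a restarted subject may or may not count in the primary variable of withdrawals due to TEAEs

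*Protocol*

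**What the plan says.** **The variable.** Section 4.1.1 lists "Subject withdrawals due to TEAEs" among the primary safety variables. The Summary (Section 1) agrees: "The primary safety variables are adverse events (AEs), subject withdrawals due to AEs, incidence of new seizure types". Both concern leaving the study.

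**The planned summaries.** Section 12.3.1 names all TEAEs, treatment-emergent SAEs and "TEAEs leading to premature discontinuation from study drug". It does not name withdrawal from the study. Section 12.2 adds a general commitment: "Descriptive statistics will be used to provide an overview of the primary, secondary, and other variable results". Section 12.3.1 leaves further detail to the SAP.

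**The liver rules.**
- Section 6.3 opens its mandatory list with "Subjects must be withdrawn from the study if any of the following events occur". Criterion 6 on that list covers ALT/AST ≥3x to <5xULN with bilirubin ≥2xULN, or ALT/AST ≥5xULN: "LCM must be immediately discontinued, and the subject withdrawn from the study". The optional withdrawal list in the same section also refers to the PDILI criteria of Section 6.3.1.
- Section 6.3.1 requires permanent IMP discontinuation at these thresholds, but states: "Subjects with PDILI should not be withdrawn from the study until investigation and monitoring are complete". It asks for the reason for withdrawal only where withdrawal applies.
- Section 10.3.1 makes a stop under 6.3.1 permanent unless another diagnosis fully accounts for the liver findings, in which case rechallenge may be considered. Section 10.3.1.2.1 sets the conditions for subjects stopped under certain PDILI criteria, "but for whom an alternative diagnosis is confirmed, can rarely restart IMP".

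**Data collection.** The reason for study withdrawal (Section 6.3) and the reason for IMP discontinuation (Section 6.3.1) are both to be recorded.

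**The concern.** Leaving the study and stopping study drug are separate events in this protocol, each with its own recorded reason. Mostly they occur together. Liver signals are where the protocol itself allows them to separate, and there one section demands withdrawal while others presuppose that the subject is still enrolled.

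Two things are at stake. The first is conduct: two sites with identical patients could act differently, each with a section to cite. The second is the count. Section 10.3.1 has every PDILI event reported as an AE, so a withdrawal for a liver signal arising on treatment belongs in the primary variable. Whether a stopped and restarted subject appears there depends on the passage the site followed, and Section 12.3.1 gives no help because it names the other quantity.

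**Working it through.** There is no stated figure to reproduce. The study is descriptive, and Section 12.8 takes its sample size from the parent study. The check is a comparison of passages, followed by one line of arithmetic.

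**Step 1: do the two rules cover the same subjects?** Criterion 6 of Section 6.3 covers (ALT/AST ≥3x to <5xULN with bilirubin ≥2xULN) or (ALT/AST ≥5xULN). The first two criteria of Section 6.3.1 are (ALT/AST ≥5xULN) or (ALT/AST ≥3xULN with bilirubin ≥2xULN). Each reduces to the same set: ALT/AST ≥5xULN at any bilirubin, plus 3x to <5xULN with bilirubin ≥2xULN. The rules therefore address identical subjects.

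**Step 2: can the rules be read together?** In criterion 6 the word for immediacy attaches to stopping LCM. Section 6.3.1 delays withdrawal until the work-up ends. A reading of stopping drug now and withdrawing later would satisfy both sentences. It does not survive two other statements: Section 6.3.1 treats withdrawal as something that may not apply, and Sections 10.3.1 and 10.3.1.2.1 allow restart. A subject who must be withdrawn cannot restart study drug within the study.

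**Step 3: how is each case counted?**

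| Case | Section 6.3 criterion 6 | Sections 6.3.1, 10.3.1, 10.3.1.2.1 | In the 4.1.1 variable? | In the 12.3.1 summary? |
|---|---|---|---|---|
| A. Threshold met, no other cause, drug stopped for good | Withdrawn | Kept until work-up complete | Yes, provided withdrawal follows the work-up | Yes |
| B. Threshold met, other diagnosis confirmed, drug restarted | Withdrawn | Still in the study | Yes under 6.3; no under the others | Unclear: no rule for a stop followed by restart |
| C. ALT/AST ≥3x to <5xULN, bilirubin <2xULN, with symptoms | Not listed | Permanent IMP stop, with possible resumption if a non-drug cause is confirmed | Not necessarily | Yes if the stop is permanent |

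Case B is the direct contradiction. Case C is not a contradiction, but it shows that the 12.3.1 quantity and the 4.1.1 variable can differ.

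**Step 4: size.** One reclassified subject changes a percentage by 100/N points. At the planned maximum of 250 subjects (Section 5.1.2) this is 100/250 = 0.4 points. At 200, the approximate number to be randomized in the parent study (Section 12.8), it is 100/200 = 0.5 points. The documents give no expected number of liver cases or restarts. If 1 to 5 subjects were affected, which is purely an assumption, the shift would be 0.4 to 2.0 points at 250, or 0.5 to 2.5 points at 200.

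**The case against.** The strongest reply has four parts.

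**The variable is already covered.** A reader might infer that a primary variable has no planned analysis. The documents do not support that. Section 12.2 promises descriptive statistics for the primary variables, with number and percentage for categorical ones, and the SAP may specify the table. What remains is narrower: Section 12.3.1 names drug discontinuation where Section 4.1.1 defines study withdrawal.

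**The two counts mostly coincide.** This stands. Section 6.3.1 sends IMP discontinuation to the Early Termination procedures of Section 8.2, and no general off-drug phase within the study is designed.

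**Safety follow-up does not depend on the answer.** A reader might infer that a subject withdrawn under Section 6.3 loses liver monitoring. That is not so. Section 6.3 requires subjects withdrawn for an AE to be followed until the event resolves or is stable, and criterion 6 requires repeat liver tests within a week. Section 10.1.3 extends follow-up to events still ongoing when a subject finishes, and Section 10.3.1.4 continues liver monitoring until values normalize, stabilize or return to Baseline.

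**Restart is rare and tightly conditioned.** This also stands. The resumption sentence in Section 6.3.1 concerns the symptomatic group, which criterion 6 does not list, and Section 10.3.1.2.1 is limited to certain criteria without saying which. The clearer support is Section 10.3.1, whose exception applies to any stop made under Section 6.3.1. Rarity limits the size of the problem but does not remove the contradiction.

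**Conclusion.** The contradiction is real and lies in the current text. Section 6.3 criterion 6 cannot be squared with the conditional withdrawal of Section 6.3.1 and the restart allowed by Sections 10.3.1 and 10.3.1.2.1. A timing reading settles only the sentence that delays withdrawal.

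The consequence for the analysis is limited. Mainly restarted subjects would change status in the primary variable, each worth 0.4 percentage points at 250 subjects, in a study without hypothesis tests. A reader might infer a large relative shift by assuming, for example, that 0.5% to 1% of 250 subjects meet the liver criteria (1.25 to 2.5) and that 5% to 10% withdraw for TEAEs (12.5 to 25), giving 1.25/25 = 5% to 2.5/12.5 = 20%. The documents give neither rate, and the calculation needs every liver case to change status. It should not be relied on.

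The point is still worth correcting: it touches a primary safety variable and a serious safety signal, and sites could lawfully follow opposite instructions for the same subject.

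**What to change.** 1. Reconcile Section 6.3 criterion 6, the PDILI reference in the optional list of Section 6.3, Section 6.3.1, Section 10.3.1 and Section 10.3.1.2.1, so that one statement says whether and when a subject stopped for a liver signal leaves the study. The choice of clinical rule is for the sponsor.
2. In Section 12.3.1, name the number and percentage of subjects withdrawn from the study due to a TEAE, as Section 4.1.1 defines the variable, and show IMP discontinuation due to a TEAE as a separate line.
3. State how a subject who stops and restarts IMP is classified on each line, following the reconciled rule.

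The cost is amendment wording and one additional table row. Both reasons are already to be recorded, so no new data collection is needed.

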### 12.3.2 Other analyses

Details of further analyses will be provided in the SAP.

## 12.4 Planned efficacy analyses

Seizure data will be summarized from diary assessments. The percent change from the combined Baseline Period in PGTCs frequency per 28 days will be summarized. Response, defined as at least a 50% reduction in PGTCs frequency per 28 days compared to the combined Baseline Period, and freedom from PGTCs during the study will also be presented descriptively.

Days with myoclonic or absence seizures are more clinically relevant endpoints; therefore, change in and percent change in days with myoclonic and/or absence seizures will be summarized. The percentage of subjects with 50% reduction in days with absence and/or myoclonic seizures per 28 days compared to the Prospective Baseline will be presented. Subjects who were seizure-free from all generalized seizures will also be tabulated.

Descriptive statistics including number of subjects, mean, SD, median, minimum, and maximum will be used to summarize continuous data including seizure frequencies per 28 days and days with seizures per 28 days. Frequency counts will be used to display categorical data, where appropriate.

## **12.5 Handling of protocol deviations**

Important protocol deviations are deviations from the protocol which potentially could have a meaningful impact on key safety outcomes for an individual subject. The criteria for identifying important protocol deviations and the classification of important protocol deviations will be defined within the project Data Cleaning Plan. To the extent feasible, rules for identifying protocol deviations will be defined without review of the data and without consideration of the frequency of occurrence of such deviations. Whenever possible, criteria for identifying important protocol deviations will be implemented algorithmically to ensure consistency in the classification of important protocol deviations across all subjects.

Important protocol deviations will be reviewed as part of the ongoing data cleaning process prior to database lock.

## **12.6 Handling of dropouts or missing data**

All data will be used to their maximum possible extent, but without any imputations for missing data for any parameter, unless otherwise specified in the SAP.

## **12.7 Planned interim analysis and data monitoring**

No interim analysis or Data Monitoring Committee is planned. However, data may be reported prior to the completion of this study to support annual reports, regulatory submissions, and publications.

## **12.8 Determination of sample size**

The sample size of this open-label extension study will be determined by the parent SP0982 study, where approximately 200 subjects are planned to be randomized.

SP0982 is an event-driven study. Up to 250 subjects may be enrolled to meet the required number of events. Baseline failures from SP0982 will also be eligible for EP0012, which may increase the sample size.

# **13 ETHICS AND REGULATORY REQUIREMENTS**

## **13.1 Informed consent**

Subject's Informed Consent/Assent must be obtained and documented in accordance with local regulations, ICH-GCP requirements, and the ethical principles that have their origin in the principles of the Declaration of Helsinki.

Prior to obtaining Informed Consent/Assent, information should be given in a language and at a level of complexity understandable to the subject in both oral and written form by the investigator (or designee). Each subject will have the opportunity to discuss the study and its alternatives with the investigator.

Prior to participation in the study, the Informed Consent/Assent form should be signed and personally dated by the subject, or his/her legal representative, and by the person who conducted the Informed Consent/Assent discussion (investigator or designee). The subject or his/her legal representative must receive a copy of the signed and dated Informed Consent/Assent form. As part of the consent/assent process, each subject must consent/assent

to direct access to his/her medical records for study-related monitoring, auditing, IRB/IEC review, and regulatory inspection.

If the Informed Consent/Assent form is amended during the study, the investigator (or the sponsor, if applicable) must follow all applicable regulatory requirements pertaining to the approval of the amended Informed Consent/Assent form by the IRB/IEC and use of the amended form.

All studies conducted at centers in the US must include the use of a Health Insurance Portability and Accountability Act Authorization form.

The subject may withdraw his/her consent to participate in the study at any time. A subject is considered as enrolled in the study when he/she has signed the Informed Consent/Assent form. An eCRF must not be started, nor may any study specific procedure be performed for a given subject, without having obtained his/her written consent/assent to participate in the study.

